2.3.1. Risk Assessment

Potential Risk of Clinical Significance	Summary of Data/Rationale for Risk	Mitigation Strategy
Investigational Product (IP) GSK3640254		
Cardiovascular (QT prolongation)	
Preclinically, GSK3640254 inhibited cardiac hERG/IKr potassium, cardiac SCN5A sodium and L-type calcium channel currents recorded from HEK 293 cells stably transfected with complementary DNA from the ion channels. In a single-dose safety pharmacology study in telemeterized dogs, increases in QT interval (up to 20 ms) occurred primarily in 1 dog given 17 mg/kg. The no observed adverse effect level (NOAEL) in the study was 12.5 mg/kg, which produced similar systemic exposures (8.79 µg/mL), 6.4 × the mean Cmax associated with the 200 mg multiple dose (1.4 µg/mL) in the FTIH study. Later, there were no GSK3640254-related effects on ECG parameters in dogs given up to 25 mg/kg/day for 4 weeks.
 
In the FTIH study, 207187 (doses up to 700 mg in SAD and 320 mg QD for 14 days in MAD), no participant exhibited QTc change from baseline >60 ms or QTc >500 ms. As described in Section 2.2.5.1, in the concentration-QTc analysis, a QTcF effect above 10 ms could be excluded for GSK3640254 plasma concentrations of up to approximately 2000 ng/mL (corresponding to doses approximately ≤200 mg QD).
	
Screening: Protocol exclusion criteria based on screening ECG parameters, screening 24-hour Holter monitor, and cardiac medical history.
 
On-Treatment: Participants will have safety ECG monitoring (at a clinically reasonable frequency) during the course of the study (see SoA, Section 1.3) with QTc stopping criteria (see Section 7.1.2).

Potential Risk of Clinical Significance	Summary of Data/Rationale for Risk	Mitigation Strategy
GI intolerance and toxicity	
Observations indicative of GI intolerance (sporadic vomiting and abnormal feces beginning on Day 1 and continuing throughout the dosing periods) occurred mainly in dogs at ≥ 1 mg/kg/day (Note: in the FTIH study, 207187, AUC = 46.4 to 73.3 $\mu\text{g}^*\text{h}/\text{mL}$; 2.6 to 4.2 \times the mean AUC associated with the 200 mg multiple dose [17.5 $\mu\text{g}^*\text{h}/\text{mL}$]). Additionally, toxicity findings of single-cell necrosis of parietal cells and/or chief cells were present in preclinical species. These findings were reversible.
 
Gastrointestinal intolerance (predominantly abdominal pain and diarrhea) was seen with a structurally related compound GSK3532795 which was evaluated through Phase 2b dosing.
 
No clinical trends in the system organ class of GI AEs have been seen across Phase 1 to 2a GSK3640254 clinical studies.
	
Screening: Protocol exclusion criterion based on pre-existing GI pathology or baseline GI signs/symptoms.
 
On-Treatment: Participants will undergo continuous evaluation for AEs during their participation in the study; there will be individual clinical stopping criteria based upon intensity of treatment-emergent AEs. A GI intolerance evaluation and monitoring plan will be available to guide investigators should GI AEs emerge (see Section 8.2.6).

Neurologic/psychiatric safety	
Two psychiatric SAEs in previous maturation inhibitor (MI) GSK3532795 clinical program (acute psychosis, homicidal/suicidal ideation) were seen at supratherapeutic doses in healthy participants in the TQT study.
 
From a neurologic and psychiatric AE summary and PK/PD analysis for GSK3532795 across all studies, Grade 1 headache and Grade 1 sleep abnormalities were the predominant AEs, with a trend for increasing neurologic and psychiatric AEs with increasing dose (based on TQT and Phase 2b studies). No exposure-response relationship was seen for select neurologic and psychiatric AEs (based on TQT and Phase 2b studies).
 
Central nervous system penetration data for GSK3532795 and GSK3640254 in rats demonstrate a similarly low brain distribution/penetration.
 
No clinical trends in the system organ class of neurologic or psychiatric AEs have been observed across the Phase 1 to 2a clinical studies.
	
Screening: Protocol exclusion criterion based on any pre-existing psychiatric condition (including results of psychological assessment) for participants. Participants will have a clinician (or qualified designee) administered C-SSRS and will be included given no positive (abnormal) response.
 
On-Treatment: Participants will undergo physical examinations and laboratory testing. In addition, participants will undergo continuous evaluation for AEs during their participation in the study; there are individual clinical stopping criteria and monitoring based upon incidence and intensity of treatment-emergent psychiatric AEs (Section 7.1.4 and Section 8.2.5).
 
Participants will be housed throughout study conduct to ensure rapid diagnosis and management of any potential event.
 
Participants will also provide responses to the C-SSRS throughout the study. Ultimately, in the event of a new onset suicidality ideation or behaviour, as determined by the investigator (in consultation with psychiatry, as needed), the participant will discontinue from the

Potential Risk of Clinical Significance	Summary of Data/Rationale for Risk	Mitigation Strategy
		study and the investigator will arrange for urgent specialist psychiatric evaluation and management. Guidance for the investigator on the management of emergent psychiatric symptoms will be available.
Rash	Across clinical studies, AEs leading to discontinuation have included urticaria and maculopapular rash.	
Screening: A physical examination, including skin assessment, will be performed at screening.
 
On-Treatment: Participants will undergo continuous evaluation for AEs during their participation in the study supplemented by the use of physical examinations.
 
Protocol includes individual participant stopping criteria (Section 7.1.4), including:
 
 • Any Grade 3 or higher rash or Grade 2 rash with evidence of systemic involvement. • Any allergic or hypersensitivity reactions.
Moxifloxacin		
GI and cardiovascular toxicity	Nausea and vomiting are the most common AEs associated with oral moxifloxacin administration. Other less common side effects include vasodilation, tachycardia, dizziness, and allergic reactions. The risk of side effects from a single dose of moxifloxacin 400 mg is estimated to be minimal.	
Screening: Protocol exclusion criteria based on pre-existing GI pathology or baseline GI signs/symptoms and screening ECG parameters and cardiac medical history.
 
On-Treatment: Participants will undergo continuous evaluation for AEs during their participation in the study; there will be individual clinical stopping criteria based upon intensity of treatment-emergent AEs. A GI toxicity evaluation and monitoring plan will be available to guide investigators should GI AEs emerge (see Section 8.2.6). Safety ECG monitoring will be performed (at a clinically reasonable frequency) during the course of the study (see SoA, Section 1.3) Participants with a history of sensitivity to moxifloxacin are excluded from the study.

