Serum pregnancy test	X
Follicle-stimulating hormone (as needed, to confirm postmenopausal status)	X
Drug, alcohol, and cotinine screen	X
Human immunodeficiency virus, hepatitis B and C screening	X
Molecular test for SARS-CoV-2 ³	X

1. A full physical examination will include at a minimum, assessments of the skin, cardiovascular, respiratory, gastrointestinal, and neurological systems.
2. May be performed either during Screening or on Day -2 upon admission.
3. Two consecutive approved molecular tests (polymerase chain reaction or antigen test). The first test should be performed ≥ 7 days prior to admission.

Time and Events Table – Part 2, Thorough QT study

Procedure	Check -in	Baseline		Periods 1, 2, and 3							W	Period 4							Follow-up		Notes	
	D -2	D -1	D1	D2	D3	D4	D5	D6	D7	D8-14 ¹	D1	D2	D3	D4	D5	D6	D7	D8	D9 ²			
Admit to clinic	X																					
Discharge from clinic																				X	Final discharge from clinic following completion of the last study procedure on Day 9 of Period 4.	
Brief physical examination	X										D14									X	An interim symptom-targeted brief physical examination will be performed at the discretion of the investigator. See Section 8.2.1 for description of the brief physical examination.	
Vital signs	X	X	X	X	X	X	X	X	X	D8, D14 only	X	X	X	X	X	X	X	X	X	Blood pressure and pulse will be measured in triplicate pre-dose on Day 1 of each period and single blood pressure and pulse will be measured on other study days. On Day 7 of each period, blood pressure and pulse to be measured before dosing and 4 and 24 hours after dosing.		
Daily temperature check	X	X	X	X	X	X	X	X	X		X	X	X	X	X	X	X	X	X	While confined to clinic.		

Procedure	Check -in	Baseline	Periods 1, 2, and 3							W	Period 4						Follow-up		Notes	
	D -2	D -1	D1	D2	D3	D4	D5	D6	D7	D8-14 ¹	D1	D2	D3	D4	D5	D6	D7	D8	D9 ²	
Safety 12-lead ECG	X	X	X	X		X	X		X	D8, D14	X	X		X	X		X	X	X	The pre-dose ECGs on Day 1 of each period will be collected in triplicate. All other ECGs will be single. On Days 1, 4, and 7, ECGs will be collected at pre-dose and post-dose at 1, 2, 3, 4, 6, and 24 hours.
Drug, alcohol, and cotinine screen	X									D14										See Appendix 2 for specific tests to be performed. Day 14 drug, alcohol, and cotinine screen required only for participants that are furloughed during the washout period.
Laboratory assessments (hematology, chemistry, urinalysis)	X									D8, D14									X	See Appendix 2 for specific tests to be performed.

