Procedure	Check -in	Baseline	Periods 1, 2, and 3							W	Period 4							Follow-up			Notes
	D -2	D -1	D1	D2	D3	D4	D5	D6	D7	D8-14 ¹	D1	D2	D3	D4	D5	D6	D7	D8	D9 ²		
Molecular Test for SARS-CoV-2	X ¹							X		D13							X				¹ The second test should be performed 24 hours prior to admission to the unit. Participants should be quarantined within the unit until the second test result is negative. Once the second test result is confirmed to be negative, they can be released into the unit and follow infection control practices. Test to be obtained every 7 days from Check-in (regardless of period or washout) while in-house.
Pregnancy test	X									D14										X	Serum testing on Day -2. Day 14 pregnancy test required only for participants that are furloughed during the washout period.
Columbia Suicide Severity Rating Scale	X									D8									X		
Randomization			X																	Period 1 only.	
Study intervention: GSK3640254 therapeutic or supratherapeutic dose, placebo, or moxifloxacin			X	X	X	X	X	X	X		X	X	X	X	X	X	X			Moxifloxacin treatment consists of GSK3640254 placebo on Days 1 through 6 with moxifloxacin on Day 7 only.	
Holter ECG recording ³		X	X						X	D8	X						X	X			

Procedure	Check -in	Baseline	Periods 1, 2, and 3						W	Period 4						Follow-up		Notes		
	D -2	D -1	D1	D2	D3	D4	D5	D6	D7	D8-14 ¹	D1	D2	D3	D4	D5	D6	D7	D8	D9 ²	
GSK3640254 PK sampling			X				X	X	X	D8	X				X	X	X	X		Blood collection for PK analysis will be collected within 40 minutes prior to dosing on Days 1, 5, 6, and 7. Day 7 post-dose samples will be collected at 0.5, 1, 2, 3, 3.5, 4, 4.5, 5, 6, 8, 10, 12, and 24 hours.
Moxifloxacin PK sampling								X		D8						X	X			Blood collection for PK analysis of moxifloxacin will be collected within 40 minutes prior to the dose on Day 7. Day 7 post-dose samples will be collected at 0.5, 1, 2, 3, 3.5, 4, 4.5, 5, 6, 8, 10, 12, and 24 hours.
AE review			←-----X-----→																	
SAE review			←-----X-----→																	
Concomitant medication review			←-----X-----→																	

AE = adverse event; D = day; ECG = electrocardiogram; PK = pharmacokinetic; SAE = serious adverse event; W = washout.

- Participants may be furloughed during the washout portion of the respective period following Day 8 procedures after discussion with and approval of the investigator. If participants are furloughed during the washout period, they should return to the clinic on Day 14 for scheduled assessments prior to initiating the next period.

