8.2.5. Suicidal Ideation and Behaviour Risk Monitoring

GSK3640254 is not a central nervous system active drug nor is it being developed for a neurologic or psychiatric condition. However, given the risk of suicidal ideation identified with a previous MI compound, GSK3532795, all participants will undergo screening using the C-SSRS administered by a clinician (or qualified designee); any positive (abnormal) response confirmed by the investigator, will exclude them from participating. Repeat assessments will be performed during the treatment phase of the study. In case of a positive (abnormal) response confirmed by the investigator, the participant will undergo immediate clinical assessment of suicidality (by the investigator or a consulting psychiatrist). Emergence of new onset suicidal ideation or a Grade 3 or higher psychiatric AE will result in immediate discontinuation and urgent specialist psychiatric evaluation and management.

The definitions of behavioral suicidal events used in this scale are based on those used in the Columbia-Suicide History Form [Posner, 2007]. Questions are asked on suicidal behavior, suicidal ideation, and intensity of ideation. Screening visit questions will be in relation to lifetime experiences and current experiences (within the past 2 months) and all subsequent questioning in relation to the last assessment.

Emergent non-suicidal psychiatric AE evaluation and management:

- Any DAIDS Grade 1 or 2 psychiatric AE: A Grade 1 or 2 psychiatric AE may result in additional unscheduled visits (in-clinic or at home) as clinically indicated. This may include a more in-depth assessment of the AE through interview, additional unscheduled clinical laboratory tests, and/or imaging. Psychiatric consultation may be required at the discretion of the investigator. Any pharmacotherapy should be discussed with the Medical Monitor.
- Any DAIDS Grade 3 or 4 psychiatric AE: As described in Section 7.1.4, a Grade 3 or 4 psychiatric AE will result in discontinuation from the study and emergency psychiatric evaluation (including potential hospitalization and pharmacotherapy as indicated).

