8.3.2. Method of Detecting AEs and SAEs

- The method of recording, evaluating, and assessing causality of AEs and SAEs and the procedures for completing and transmitting SAE reports are provided in Appendix 6.
- Care will be taken not to introduce bias when detecting an AE and/or SAE. Open-ended and non-leading verbal questioning of the participant is the preferred method to inquire about AE occurrence. Participants will be questioned prior to each dose of study intervention.

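### Part 2 participants can be furloughed from Day 8 to Day 14, but no C-SSRS is scheduled on their return before seven more dosing days; a furlough-only Day 14 C-SSRS would close this small gap cheaply

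*Protocol*

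**What the plan says.** **Housing and C-SSRS.** In Protocol Section 2.3.1, the neurologic/psychiatric row says under its on-treatment heading: "Participants will be housed throughout study conduct to ensure rapid diagnosis and management of any potential event". The same cell says: "Participants will also provide responses to the C-SSRS throughout the study". It also lists physical examinations, laboratory tests, continuous adverse event evaluation, individual stopping criteria, urgent psychiatric referral and guidance for the investigator.

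**Furlough.** A footnote to the Part 2 table in Section 1.3 says: "Participants may be furloughed during the washout portion of the respective period following Day 8 procedures after discussion with and approval of the investigator". For those who leave, "they should return to the clinic on Day 14 for scheduled assessments prior to initiating the next period".

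**Tests added because of furlough.** The notes to two rows of that table say "Day 14 drug, alcohol, and cotinine screen required only for participants that are furloughed during the washout period" and "Day 14 pregnancy test required only for participants that are furloughed during the washout period".

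**C-SSRS schedule in Part 2.** The row has a mark at check-in (Day -2), D8 alone in the washout column of Periods 1 to 3, and one mark in the Period 4 follow-up columns. It has no Day 14 entry and no note.

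**How each repeat C-SSRS is asked.** Section 8.2.5 puts "all subsequent questioning in relation to the last assessment".

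**The concern.** The sponsor treats suicidality as a risk carried over from the earlier maturation inhibitor. Section 2.2.1 reports two psychiatric SAEs in that compound's thorough QT study, at supratherapeutic doses in healthy participants. Part 2 is the same kind of study.

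A furloughed participant loses one listed mitigation, housing, for several days. The schedule recognises that time away calls for checks on return, because it adds two tests for that reason alone. The instrument chosen for suicidality is not among them. Ideation that began during furlough would be covered by the next C-SSRS, but that C-SSRS is read only after the next period's doses have been given.

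At stake is whether a structured suicidality check comes before or after re-dosing. Sample size, error rates and the QTc analysis are not involved.

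**Working it through.** The plan gives no figure to reproduce on this point. The check sets the texts side by side and adds simple counts.

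**1. What happens on Day 14 (Section 1.3, Part 2 table)**

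| Assessment | Washout entry | Who has it on Day 14 |
|---|---|---|
| Brief physical examination | D14 | everyone |
| Vital signs, safety ECG, laboratory tests | D8, D14 | everyone |
| Drug, alcohol and cotinine screen | D14 | furloughed only |
| Pregnancy test | D14 | furloughed only |
| C-SSRS | D8 | no one |

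**2. Interval between scheduled C-SSRS.** Assume that Day 14 is followed directly by Day 1 of the next period.
- Day 8 to Day 14: 6 days, the longest time away in one washout.
- Day 8 to the next Day 1: 7 days.
- Day 8 to the next Day 8: 14 days, with seven dosing days in between.
- Into Period 4 the interval is 14 days, or 15 if the follow-up mark belongs to Day 9; the table as read does not settle this.

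**3. Upper bound on time away.** In-clinic schedule: 2 + 3 × 14 + 9 = 53 days. Three full furloughs: 3 × 6 = 18 days. 18/53 = 34%. This assumes that a participant takes all three furloughs in full.

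**4. Which washouts touch active drug.** The 12 sequences have 12 × 3 = 36 washouts.
- After T or ST: 18 (9 of them after ST).
- Before T or ST: 24 active cells − 6 in Period 1 = 18.
- Directly between two active periods: 6 (T to ST in sequences 1, 7 and 9; ST to T in 4, 6 and 12). 6/36 = 17%.
- Next to no active period: 36 − 18 − 18 + 6 = 6.

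**5. Drug remaining during furlough.** Input: half-life 22 to 28 h (Section 2.2.3). Assumption: simple exponential decline, fraction = 0.5^(t/half-life).
- 24 h after the last dose (Day 8): 0.5^(24/22) = 0.47 and 0.5^(24/28) = 0.55.
- 168 h after it (Day 14): 0.5^(168/22) = 0.005 and 0.5^(168/28) = 0.016.

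After an active period, furlough can therefore start with about half the concentration still present. By Day 14 almost none is left.

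**6. Extra questionnaires if Day 14 is added.** 3 × 42 = 126 if all 42 participants complete and take every furlough; 3 × 34 = 102 for 34 completers.

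**The case against.** The strongest reply is that much remains in place.
- A C-SSRS is scheduled on Day 8, and furlough follows Day 8 procedures and needs investigator approval.
- The returning participant is examined on Day 14.
- Section 8.3.2 says "Participants will be questioned prior to each dose of study intervention", so questions are put before the first dose of the next period.
- New onset suicidal ideation is a stopping criterion in Section 7.1.4 whether or not a C-SSRS finds it.
- Section 8.2.5 foresees unscheduled visits, including at home, for milder psychiatric events.
- Psychiatric exclusions apply at screening.

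All of this stands. It limits the point to the absence of a structured check on return. The limit is real, because the adverse event questions are meant to be open-ended and non-leading, and the brief physical examination covers skin, lungs, cardiovascular system and abdomen.

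The housing sentence can also be defended. It sits under an on-treatment heading, Section 2.3.3 speaks of confinement after dosing, and the schedule states the furlough rule clearly, so no site would be misled. Sections 1.1 and 4.1 also describe confinement without mentioning furlough. This largely stands: the wording conflict alone is close to clerical.

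Two further replies carry weight. Half of the washouts (18 of 36) precede placebo or moxifloxacin, so the doses that follow are often not active drug. The earlier compound's psychiatric findings have not been reproduced with GSK3640254 (Section 2.2.1). That reassurance has a limit, however. Repeat dosing in healthy volunteers stopped at 320 mg daily (Section 2.2), with 2154 ng/mL (Section 2.2.5.1). The supratherapeutic target is about 4.4 µg/mL (Section 4.3), and 4400/2154 is about 2.0.

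Finally, the absence of a C-SSRS on Days 1 to 7 applies to every Part 2 participant, housed or not. It is not the point here.

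**Conclusion.** The point holds as a minor patient-safety improvement. After a furlough of up to about 6 days, no structured suicidality check is scheduled until the next period's seven dosing days are over, although the participant is already in the clinic on Day 14.

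A reader might infer that housing and the C-SSRS are the only psychiatric safeguards and that furlough defeats both. The documents do not support that. The risk table lists several others, and each repeat C-SSRS reaches back over the furlough. A reader might also take the housing sentence as a serious contradiction. Its placement and the explicit schedule make it imprecise wording.

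The day counts rest on 14-day periods, and the 34% figure on full use of every furlough. The residual-drug figures rest on exponential decline and apply only after an active period. The furlough rate is not stated, so the number of participants affected cannot be given. The QTc analysis does not change.

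**What to change.** 1. **Section 1.3, Part 2 table, C-SSRS row.** Change the washout entry from 'D8' to 'D8, D14'. Add a note that the Day 14 C-SSRS applies only after a furlough and that its result is reviewed before the Day 1 dose of the next period. Apply it whatever the treatment, so that the blind is kept.
2. **Section 2.3.1, housing sentence (clarification).** Keep the sentence and add an exception: in Part 2, with the investigator's approval, participants may leave between the end of Day 8 procedures and Day 14 of Periods 1 to 3.

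Optionally, Section 7.1.3 could state that a positive Day 14 response triggers the same clinical assessment as one during treatment. Furlough itself can stay.

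The cost is at most one more questionnaire per furloughed washout, within the upper bound of 126, with no added visit.

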2.3.2. Benefit Assessment

This is a study in healthy participants; no medical benefit will be derived by participants' participation.

2.3.3. Overall Benefit: Risk Conclusion

Given the preclinical profile of GSK3640254, the clinical profile of a structurally similar MI (GSK3532795), the clinical data gathered from Phase 1 and 2a studies, and the planned clinical procedures and evaluations in this study, the potential risks to participants receiving GSK3640254 are low, evaluable, and manageable.

Moxifloxacin is commonly used in clinical practice and has a well-characterized and acceptable safety profile. Given that only healthy participants will be enrolled and that participants will be confined to a clinical facility after dosing, the safety risk of participation in this study is expected to be low. To minimize risk further, the protocol contains exclusions relevant to the study intervention.

